- Changed the modified intent-to-treat (mITT) population to not require 1 postbaseline measurement so it is the same as the safety population
- Analysis datasets were altered to only include full analysis set (FAS) and efficacy analysis set (EAS)
- Removed the per-protocol (PP) population and all associated analyses
- Removed description of calculation of type 2 diabetes mellitus (T2DM) duration as it is in data standard
- Changed thresholds of glycated hemoglobin (HbA1c) targets for categorical analyses
- Corrected classification categories for calcitonin
- Removed all subgroup analyses unless needed post-hoc

4. Study Objectives

4.1. Primary Objectives

The primary objective of this study is to demonstrate that at least one LY3298176 titration scheme is superior to placebo in HbA1c reduction at 3 months in patients with T2DM inadequately controlled with diet and exercise alone, or treated with a stable dose of metformin.

4.2. Secondary Objectives

The secondary objectives are to compare each titration scheme to placebo at 3 months for the following secondary efficacy parameters:

- proportion of patients achieving HbA1c target of <7.0%
- the change in fasting blood glucose (FBG) (central laboratory) from baseline
- the change in body weight from baseline
- the change in waist circumference from baseline
- incidence of treatment-emergent adverse events (TEAEs) and serious adverse events (SAEs)
- incidence of nausea, vomiting, and diarrhea
- discontinuation of study drug due to adverse events (AEs)
- incidence and rate of hypoglycemia (severe, total, documented symptomatic, and nocturnal)
- incidence of anti-LY3298176 antibodies

4.3. Exploratory Objectives

- To compare each titration scheme to placebo at 3 months for effect on self-monitoring blood glucose (SMBG) profile.

5. Study Design

5.1. Study Design and Treatment

Study I8F-MC-GPGF (GPGF) is a randomized, double-blind, parallel, placebo-controlled, Phase 2, multicenter, study designed to examine the efficacy and safety of once-weekly LY3298176, compared with placebo in patients with T2DM.

The design for Study GPGF is illustrated in [Figure 5.1](#).

[figure not shown]

Figure 5.1. Study design for I8F-MC-GPGF.

Study procedures and timing for the lead-in, blinded treatment, and follow-up phases are outlined in the schedule of events ([Appendix 1](#)). Eligibility for this study will be determined at the screening visit (Visit 1).

5.2. Treatment Assignment

A unique 4-digit patient number will be assigned to each patient when the patient signs the informed consent form (ICF).

Patients will be assigned to placebo, or one of three LY3298176 dose groups. Patients who meet all criteria for enrollment will be randomized at Visit 3 and assigned to their respective treatment arms via interactive web response system (IWRS) using the following stratification variables: baseline HbA1c (<8.5%, ≥8.5%), metformin use (Yes, No), and body mass index (BMI) (<30, ≥30). There will be equal randomization to the treatment arms (1:1:1:1). However, placebo patients will be randomized such that a portion will be randomized to each cohort to receive the same dose volume as that cohort in order to maintain the study blind.

The randomization scheme will be performed using IWRS to ensure balance between treatment arms.

5.3. Determination of Sample Size

Approximately 92 patients will be randomized to placebo or to one of three LY3298176 titrations arms, assuming a 13% dropout rate, resulting in approximately 20 completers per arm.

Assuming a standard deviation of 1.1, 20 patients per arm will provide at least 90% power to detect a statistically significant difference between LY3298176 titration schemes to placebo with a dose response assumption as shown in [Table 5.1](#).

Table 5.1. Dose-Response Assumption Used in Sample Size Determination

	Placebo	LY 12 mg	LY 15 mg-1	LY 15 mg-2
CFBL HbA1c (%)	-0.2%	-1.4%	-1.5%	-1.5%

Abbreviations: CFBL = change from baseline; HbA1c = glycated hemoglobin; LY = LY3298176.

6. A Priori Statistical Methods

6.1. General Considerations

Statistical analysis of this study will be the responsibility of Lilly or its designee. Any change to the statistical methods described in the protocol will require an amendment only if it changes a principal feature of the protocol. Any other change to the statistical analyses and the justification for the change will be described in the SAP and/or clinical study report (CSR). Additional exploratory analyses of data may be conducted, as deemed appropriate, without further changes made to the protocol or SAP even after the database lock (DBL).

No adjustments for multiplicity will be performed.

All tests of treatment effects will be conducted at a 2-sided alpha level of 0.05 and/or 2-sided 95% confidence interval (CI) unless otherwise stated. This is different from what is stated in the protocol.

The baseline visit will be Visit 3. For all variables, if baseline data are not available or are missing, the last nonmissing measurement taken prior to Visit 3 will be used for the baseline measurement.

All efficacy and safety data will be summarized by each treatment group at each scheduled visit unless otherwise indicated. Imputed data may be applied in model-based data analysis, but will not be used in data listing.

6.1.1. Analysis of Repeated Measures

The mixed model for repeated measures (MMRM) using restricted maximum likelihood (REML) will be used to fit change from baseline values at all scheduled visits. The model will include the treatment group, strata (that is, baseline HbA1c category, baseline BMI category, and metformin use [yes, no]), visit, and treatment-by-visit interaction as fixed effects, baseline value of the dependent variable as a covariate, and patient as a random effect. If the analysis is on the primary endpoint, baseline HbA1c category will not be included in the model in addition to the continuous covariate of baseline HbA1c. To model the covariance structure within patients, the unstructured covariance matrix will be selected initially. If the unstructured covariance structure leads to nonconvergence, the following covariance structures will be tested in order:

- Toeplitz with heterogeneity
- autoregressive with heterogeneity
- compound symmetry with heterogeneous variances
- Toeplitz
- autoregressive
- compound symmetry without heterogeneous variances
- compound symmetry

The first covariance structure that converges will be used.

Kenward-Roger method will be used to estimate the denominator degrees of freedom and the restricted maximum likelihood approach will be used to determine the model estimates.

The MMRM model will present least squares (LS) mean estimates for each scheduled week by treatment group and 2-sided 95% CIs for mean changes from baseline within and (when warranted) between treatments. T-statistics corresponding to the Type III sums of squares for the differences in the LS means will be used to obtain p-values for treatment group comparisons.

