10.3.3. Efficacy Analyses

10.3.3.1. Primary Analyses

The primary outcome is the difference in HbA1c change from baseline between treatment groups based on the mITT population at the planned end of the treatment period of 3 months. The primary analysis model will be a mixed model for repeated measures (MMRM) for HbA1c change from baseline to 3 months in the mITT population with treatment, visit, treatment-by-visit, baseline BMI category, and metformin use (yes, no) as fixed effects, and baseline HbA1c as a covariate. The dependent variable will be the postbaseline change from baseline values. An unstructured covariance structure will be used to model the within-patient errors. If this model fails to converge, the following covariance structures will be tested in order:

- toeplitz with heterogeneity
- autoregressive with heterogeneity, by visit
- compound symmetry with heterogeneous variances by visit
- toeplitz
- autoregressive
- compound symmetry without heterogeneous variances, by visit
- compound symmetry.

The first covariance structure that converges will be used.

The treatment p-value will be used as evidence of difference between active drug and placebo, while the comparison of least-squares (LS) means versus placebo (unadjusted for multiple comparisons) will provide magnitude and significance of this difference. The primary analysis model, MMRM, will be repeated using the PP population. If the conclusion differs from that of the mITT population, the data and analyses will be further investigated.

Descriptive statistics by treatment for HbA1c and HbA1c change from baseline at the 12-week endpoint will be presented using all observed data with no imputations and no elimination of patients with protocol violations. The descriptive statistics will be presented by visit and will include sample size, mean, SD, median, minimum, and maximum.

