6.3. Analysis Populations and Datasets

Three patient populations are defined for the analyses in this study with detailed information listed in [Table 6.1](#). Analyses datasets specifying data exclusion are listed in [Table 6.2](#).

Unless otherwise specified, listings will include FAS for all randomized patients; safety analyses, except for hypoglycemia events, will be conducted in the mITT population with the FAS; and efficacy analyses including primary and key secondary efficacy analyses will be conducted in the mITT population with the EAS.

Table 6.1. Analysis Populations

Population	Definition
All Entered	All patients who signed informed consent forms (ICFs)
All randomized (Intent-to-Treat [ITT])	All patients who were randomized to a treatment arm
Safety Population (Modified Intent-to-Treat [mITT])	All randomized patients who have taken at least 1 dose of the study medication. This is different from what is stated in the protocol. Analyses using the mITT population will be presented by the planned treatment group.

Table 6.2. Analyses Datasets

Analysis Dataset Name	Description
Full Analysis Set	All data available
Efficacy Analysis Set	Only include data on study medication without using rescue medication, i.e., excluding data after rescue medication initiation or after study treatment discontinuation (last dose date +7).

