6.9.1. Primary Outcome and Methodology

The primary outcome is the difference in HbA1c change from baseline between treatment groups at the end of the treatment period of 12 weeks. The primary analysis model will be a MMRM for HbA1c change from baseline to 12 weeks described in Section 6.1.1. The treatment p-value will be used as evidence of difference between active drug and placebo, whereas the comparison of LS means versus placebo (unadjusted for multiple comparisons) will provide magnitude and significance of this difference.

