Study Day/(dose number)			0/(1)	7/(2)	14/(3)	28/(5)	31-34	56/(9)	59-62	84	105	
Visit Window (days)		+7	0	0	±2	±3		±3		±3	±3	
Diagnostics (Efficacy)												
Calcitonin	X									X		X
HbA1c	X		X			X		X		X	X	X
Fasting glucose	X		X			X		X		X	X	X
Total and active GLP-1/GIP			X			X		X		X	X	
7-point SMBG			X ^l							X ^l		
PK ^k						X		X		X	X	X
Immunogenicity			X			X		X		X	X ^l	X
Nonpharmacogenetic stored samples			X							X		

Abbreviations: AE = adverse event; BG = blood glucose; BP = blood pressure; ECG = electrocardiogram; eGFR = estimated glomerular filtration rate;

ET = Early Termination; FSH = follicle-stimulating hormone; GIP = glucose-dependent insulinotropic peptide; GLP-1 = glucagon-like peptide-1;

HbA1c = hemoglobin A1c; IWRS = interactive web response system; PK = pharmacokinetics; PR = pulse rate; SMBG = self-monitoring of blood glucose;

T = telephone visit; TE-ADA = treatment emergent anti-drug antibodies; Term. = termination.

- a Telephone visits occur during the week following a dose escalation and should be done 3 to 6 days after a site visit for dose escalation and administration. At telephone visits, the sites should call the patient, ask how the patient is, and ask whether the patient would like to come to the site for assistance with the next study drug dilution and administration. Sites should also remind patients to write down any AEs in their diaries at the telephone visits (as well as at all site visits).
- b Visit should occur approximately 1 week after the last dose (Dose 12).
- c Additional physical examinations may be performed throughout the study if determined necessary due to patient symptoms.
- d Visit should occur 4 weeks after the last dose of study drug or 3 weeks after Visit 10.
- e ECGs should be collected prior to all blood draws and study drug administrations. Local ECGs will be collected for screening (Visit 1) and Early Termination. Centralized ECGs, collected in supine position and in triplicate, should be collected for all other designated visits.
- f Screening laboratory tests include serum hepatitis B surface antigen (Ag), hepatitis C antibody (Ab), and human immunodeficiency virus (HIV) Ab tests for all patients (see [Appendix 2](#)).

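### The primary MMRM gives baseline HbA1c a single slope for all visits; if that slope steepens during titration, the Week 12 contrast is under-adjusted and loses some precision, which a baseline-by-visit term would recover cheaply

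*SAP*

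**What the plan says.** SAP 6.9.1 fixes the primary analysis: "The primary analysis model will be a MMRM for HbA1c change from baseline to 12 weeks described in Section 6.1.1". That section enters "visit, and treatment-by-visit interaction as fixed effects, baseline value of the dependent variable as a covariate", alongside treatment and the strata. Protocol 10.3.3.1 lists the same kind of model: "treatment, visit, treatment-by-visit, baseline BMI category, and metformin use (yes, no) as fixed effects, and baseline HbA1c as a covariate". The protocol synopsis agrees, and neither document adds a baseline-by-visit term anywhere.

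Three further provisions matter:

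- For the primary endpoint, "baseline HbA1c category will not be included in the model in addition to the continuous covariate of baseline HbA1c". The single slope is then the only adjustment for baseline HbA1c.
- For the within-patient errors, "the unstructured covariance matrix will be selected initially".
- The efficacy analysis set (SAP Table 6.2) works by "excluding data after rescue medication initiation or after study treatment discontinuation (last dose date +7" days), so in practice the primary model fits Weeks 4, 8 and 12.

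Randomization is stratified on HbA1c at 8.5% (SAP 5.2). A supportive ANCOVA on the LOCF endpoint (SAP 6.9.1.1) estimates its own endpoint slope.

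**The concern.** Titration is forced. Protocol Table GPGF.3 has doses of 2.5 to 5 mg in Weeks 0-3, 7.5 to 10 mg in Weeks 4-7, and 12 or 15 mg only from Week 8. Much of the HbA1c fall can be expected after Week 4, and patients who start higher usually have more room to fall, so the regression of change on baseline may well be steeper at Week 12 than at Week 4. The model allows the treatment effect to grow over visits but holds the baseline slope constant.

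Under an unstructured covariance, the common slope is a precision-weighted combination of the visit slopes. If Week 4 is much the least variable visit, it dominates, and the Week 12 contrast is adjusted with too flat a slope. At stake are the width of the Week 12 interval for each scheme, with about 20 completers per arm, and the correction of chance imbalance in baseline HbA1c.

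**Working it through.** **The plan's own figure.** SAP 5.3 gives SD 1.1, 20 per arm and a smallest difference from placebo of -1.4 - (-0.2) = -1.2. The SE is 1.1 × √(2/20) = 0.348. Two-sided 0.05 power is Φ(1.2/0.348 - 1.96) = 0.932 (0.919 to 0.926 with t quantiles). With 13% dropout, 20/0.87 rounds up to 23 per arm, or 92. The stated power and sample size reproduce.

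**Inputs not in the documents (assumed).** Baseline SD 0.9; total Week 12 SD of change 1.1, read as unadjusted; residual correlations 0.8 (Weeks 4-8), 0.9 (8-12) and 0.65 (4-12); residual SD ratios and visit slopes as tabulated.

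**Formulas.** With V the residual covariance over the three visits and b the visit slopes:

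- weights w = V⁻¹1 / (1′V⁻¹1); fitted common slope b_c = w′b
- Week 12 residual variance = 1.1² - b₁₂² × 0.9²
- relative increase in model-based Week 12 variance = (b₁₂ - b_c)² × 0.9² / residual variance
- imbalance left uncorrected = |b₁₂ - b_c| × baseline difference

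**Weights (Weeks 4, 8, 12).** SD ratios 0.5/0.8/1: 1.31, -0.40, 0.09. Ratios 0.85/0.95/1: 0.83, -0.28, 0.45. Equal SDs: 0.58, -0.23, 0.65.

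**Worked case.** Slopes -0.20/-0.40/-0.50 with ratios 0.5/0.8/1. The common slope is 1.31(-0.20) - 0.40(-0.40) + 0.09(-0.50), about -0.148 before rounding of the weights. Residual variance is 1.21 - 0.2025 = 1.0075. The increase is 0.352² × 0.81/1.0075 = 10%, so the SE rises about 5%.

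| True slopes, Weeks 4/8/12 | 0.5/0.8/1: common slope, variance | 0.85/0.95/1 | Equal SDs |
|---|---|---|---|
| -0.20/-0.25/-0.30 | -0.19, +0.9% | -0.23, +0.3% | -0.25, +0.2% |
| -0.15/-0.30/-0.40 | -0.11, +6% | -0.22, +2% | -0.28, +1% |
| -0.20/-0.40/-0.50 | -0.15, +10% | -0.28, +4% | -0.35, +2% |
| -0.10/-0.30/-0.50 | -0.06, +16% | -0.22, +6% | -0.31, +3% |
| -0.20/-0.40/-0.60 | -0.16, +17% | -0.32, +7% | -0.41, +3% |

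With a small Week 4 SD the fitted slope lies near or below the Week 4 slope in size. With equal SDs it lies between the Week 4 and Week 12 slopes.

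**Simulation of the worked case.** 6000 trials, 4 × 20 complete cases, stratified on HbA1c at 8.5%; restricting to the 7.0-10.5% entry range gave a realized baseline SD of 0.81.

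| | Visit-specific slope | Common slope |
|---|---|---|
| Mean estimate (true -1.20) | -1.202 | -1.201 |
| Empirical SD | 0.316 | 0.321 |
| Model SE | 0.317 | 0.330 |
| Power | 0.964 | 0.954 |

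Empirical variance rises by (0.321/0.316)² - 1 = 3%, and model-based variance by (0.330/0.317)² - 1 = 8%. For the second, fourth and fifth slope sets in the first table, stratified runs with the same SD ratios gave empirical increases of 2%, 6% and 5%.

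**Imbalance.** Stratification cuts the SD of the arm difference in baseline HbA1c from about 0.26 to 0.15, a mean absolute difference of 0.15 × 0.80 = 0.12 (0.14 in a second set of runs). The slope shortfall in the 6-17% scenarios is 0.29 to 0.44, which leaves 0.29 × 0.12 = 0.03 to 0.44 × 0.14 = 0.06 HbA1c points uncorrected.

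**Power.** By the normal formula, power in the worked case is 0.966 with a visit-specific slope and 0.950 with a common one. If 1.1 is instead the adjusted SD, 0.932 falls to 0.912. At the steepest corner tried (slopes -0.15/-0.40/-0.60, baseline SD 1.0), the SE rises 14%, and power is 0.88 if 1.1 is the adjusted SD.

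**The case against.** The strongest reply is that the size hangs on inputs the plan does not give. A reader might infer that the Week 12 contrast is in effect adjusted with the Week 4 slope. That needs a Week 4 residual SD clearly below the Week 12 SD. This is plausible early in titration, but the documents supply only the overall 1.1. With equal SDs, in the scenarios with appreciable steepening, the fitted slope lies nearer the Week 12 value and the variance loss is 1-3%. This objection stands.

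A reader might also turn the variance increase into patients lost. The model-based figure describes interval width; stratification already removes much of the imbalance, and the estimate's actual spread grows only 2-6%. This stands too.

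The titration argument also does not apply to placebo. If only the active arms' slopes steepen, the model-based increase in the three scenarios of 6%, 16% and 17% falls to about 3%, 8% and 8%, and the empirical increase to 0-2%, even with a small Week 4 SD.

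Finally, the LOCF ANCOVA has its own endpoint slope. That helps little: it is supportive only, and for dropouts it carries forward values from lower doses.

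None of this removes the asymmetry. If the slopes steepen the common slope costs precision, and if they do not the extra term costs almost nothing.

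**Conclusion.** The point holds as a cheap efficiency improvement. Both documents fit one baseline HbA1c slope over Weeks 4, 8 and 12, and nothing else in the primary model carries baseline HbA1c. If the slope steepens, model-based Week 12 variance is larger by about 0-3% when residual SDs are equal or slopes nearly flat, and by 6-17% when slopes steepen and the Week 4 residual SD is half the Week 12 SD. Most of that is a mildly conservative interval. A typical chance imbalance leaves roughly 0.03-0.06 HbA1c points uncorrected, against assumed effects of 1.2 to 1.3.

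Two stronger inferences are not supported. The primary estimate is not biased unconditionally: the residual error is conditional on chance imbalance and averages to zero over randomization. Nor is the trial shown to be underpowered: power stays at or above 90% except with the steepest slopes and 1.1 read as an adjusted SD (0.88 to 0.90).

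These sizes rest on the assumed slopes, SDs and correlations, on complete data, and on simulated stratification by HbA1c category alone.

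**What to change.** In SAP 6.1.1, add a baseline-value-by-visit interaction to the primary MMRM, so that it contains treatment, visit, treatment-by-visit, baseline, baseline-by-visit, BMI category and metformin use. Record it in the SAP as a difference from Protocol 10.3.3.1; SAP 6.1 allows changes that do not alter a principal feature of the protocol to be made there.

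The same term can go into the weight, FBG and waist circumference models, which share Section 6.1.1. No gain was computed for those, and they also keep the HbA1c stratum.

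The cost is one line of text and two parameters (three visit slopes instead of one). If the slopes are truly equal, simulation puts the price at about 1% of the Week 12 variance.

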6.1.2. Analysis of Covariance Model for Change from Baseline Endpoints

The analysis of covariance (ANCOVA) models of change from baseline to Week 12 efficacy endpoints will include treatment group, strata (that is, baseline HbA1c category, baseline BMI category, and metformin use [yes, no]) as fixed effects and baseline measurement as a covariate. If the analysis is for the primary endpoint, baseline HbA1c category will not be included in the model in addition to the continuous covariate of baseline HbA1c.

The ANCOVA will present LS mean estimates and 2-sided 95% CIs for mean changes from baseline within and (when warranted) between treatments. T-statistics corresponding to the Type III sums of squares for the differences in the LS means will be used to obtain p-values for treatment group comparisons.

6.2. Patient Disposition

All patients who discontinue the study will be identified, and the extent of their participation in the study will be reported. If known, a reason for their discontinuation will be given. The primary reasons for discontinuation will be listed and will be summarized by treatment. The percentage of patients discontinuing from each treatment will be compared using the Fisher's exact test.

Patient statuses at the end of the 12-week treatment period will be summarized, displaying the numbers of patients:

- entered
- screen failed, along with the primary reason for screen failure
- randomized
- randomized and not treated
- permanently discontinued from treatment, along with the primary reason for treatment discontinuation
- discontinued from study, along with the primary reason for study discontinuation
- completed 12 weeks blinded treatment
- completed study

The summary of status at the end of the 12-week treatment period will count patients by randomized treatment group and overall, except that “Entered” and “Screen failures” only apply to the overall entered population. Entered is defined as signing an informed consent form (ICF). The percentage of patients discontinuing from each treatment will be compared using the Fisher’s exact test.

